8.3 Adjustment of P values for Multiple Testing

It is intended that no formal adjustment for multiple significance testing will be made.

8.4 Missing Data

AspECT

A phase III randomised study of Aspirin and Esomeprazole chemoprevention in Barrett's metaplasia

Funded by CR-UK, MRC, UHL and NCI

ISRCTN No.85156844

It is expected that all data will be available to make the primary objective analysable on all patients randomised. Nonetheless, patients will be lost to follow-up and this will be summarised as outlined above to allow a reader to adjust their interpretation of the results accordingly.

The secondary endpoints will not all be complete and some analysis will be done on a subgroup of the patients who have the data. In these cases the patients in the analysis and those left out will be described.

We do not expect to impute any data for the analysis in this plan.

8.5 Pre-specified Subgroup Analysis

The analysis applies to males and females (planned to be 500) combined but will be repeated on males only and on just the females.

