## 14.1 Final analysis

This trial completed recruitment within 4 years of opening to recruitment. The DSMC will decide the time point for the final analysis. Final analysis is planned 8 years after the end of patient recruitment and will be guided by the fulfilment of the sample size calculation to be when there are at least 200 events and a median of at least 5 years follow up.

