2.1 Objectives

Primary OBJECTIVES:

- To assess whether intervention with aspirin results in a decreased rate of all causes of mortality or conversion rate from Barrett's metaplasia (BM) to adenocarcinoma or high grade dysplasia.
- To assess whether high dose PPI therapy results in a decreased rate of all causes of mortality or conversion rate from Barrett's metaplasia to adenocarcinoma or high grade dysplasia.

Secondary OBJECTIVES:

- To assess whether intervention with aspirin results in decreased high-grade dysplasia, in decreased all cause mortality, in decreased oesophageal cancer incidence and in decreased cause-specific mortality when each is considered separately
- To assess whether intervention with high dose PPI results in decreased high-grade dysplasia, in decreased all cause mortality, in decreased oesophageal cancer incidence and in decreased cause-specific mortality when each is considered separately
- To assess whether there are clinical and molecular risk factors which can be identified in BM for the development of Barrett's Adenocarcinoma (BA).
- To assess the cost effectiveness of aspirin and/or PPI treatment in the prevention of BA.
- To assess whether intervention with PPI and/or aspirin induces changes in the expression of molecular markers for BA. To assess the genomics of aspirin sensitivity (efficacy and side effects)
- To assess how quality of life is affected by the different treatments.
- To assess what the biological risk factors are for cardiac disease and aspirin resistance.
- To assess gender differences in outcomes.

Exploratory aims

1. To assess aspirin's role on the development of colorectal adenomas and cancer.
2. To collect and bank samples for use in future ethically approved studies

AspECT

A phase III randomised study of Aspirin and Esomeprazole chemoprevention in Barrett's metaplasia

Funded by CR-UK, MRC, UHL and NCI

ISRCTN No.85156844

Exploratory uses of the data

1. Describe Barrett's length over repeat biopsies and investigate a change in length from baseline to 2 years between treatment groups.
2. Can intervention with aspirin result in a lower stage of adenocarcinoma ?
Can intervention with PPI result in a lower stage of adenocarcinoma ?
3. Does adjustment for Oesophagectomy, Ablation therapy, Endoscopic mucosal resection change the treatment effect ?

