2.5.2 Sample Size – original statement

A total of 5000 patients (1250 in each intervention group) will allow us to detect a difference in conversion rates of 0.22% per year between the PPI and aspirin intervention. The sample size required was calculated (pre CSM involvement) using nQuery Advisor® Release 4.0 based on the following:

Patients will be recruited over 2 years and followed up for a further 8 years. Exponential time to conversion with a constant event rate of at least 0.76% per year

Conversion hazard ratio (drug response) of control to treatment is 1.4

Power = 80% (2-sided test at 5% level of significance).

No interaction between the effects of aspirin and PPI interventions.

A 10% loss to follow-up from Office of National Statistics flagging

A 20% non-compliance with medication

Calculations adjusted for competing causes of mortality. A further proportion may take their medication but be lost to follow-up as they do not return their questionnaire and/or attend for surveillance endoscopy. This will not affect the primary outcome as all cause mortality and conversion to BA will be assessed by the Office of National Statistics, which has almost complete follow-up of registered subjects (we have conservatively assumed a 90% follow-up rate).

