2.5.3 Exploratory sample size statement October 2008

Due to protocol amendments and an expected restriction on the number of patients to be recruited, an exploratory sample size is presented at the request of the Funders. Since the trial will recruit until end Dec 2008 in the UK and possibly until the end of June in Canada rather than to the number calculated in the original sample size, this calculation should be considered as a guide to the power and treatment effect size the trial should achieve.

This exploratory sample size is calculated as per the original sample size, but with

- Annual rate of conversion of 1% (allowing for the composite primary endpoint of all cause mortality and conversion to adenocarcinoma and conversion to high grade dysplasia.)

Justification: Using the National Statistics figures for 2005 based on the age and gender structure of the first 2046 patients recruited to AspECT gives a mortality rate in a year of 1.16%.

Using the UK Barrett's conversion rate to adenocarcinoma of at least 0.98% per year without treatment for 60% of the sample and 40% with a lower conversion rate of 0.66% (due to being

AspECT

A phase III randomised study of Aspirin and Esomeprazole chemoprevention in Barrett's metaplasia

Funded by CR-UK, MRC, UHL and NCI

ISRCTN No.85156844

female, have tongues of Barrett's metaplasia or only 1cm of Barrett's, or being <45 years old. Differing rates are not published for these patients so a rate of two thirds the UK conversion rate has been used) ie 0.85% conversion rate without treatment over the whole sample.

No good estimates of rates for conversion to high grade dysplasia for the UK could be found.

In this population, it is unlikely that the event rate for the composite primary endpoint in the control arm will be less than 1%.

- HR as in colorectal cancer
- No adjustment for compliance
- the follow-up increased to 10 years

Apart from limited recruitment and checking the event rate using the age/sex structure, no information or estimates from the current trial are used.

A total of 2224 patients (196 events) (approximately 556 in each intervention group) will allow us to detect a difference in conversion rates of 0.34% per year between low dose and high dose PPI and aspirin or no aspirin. This sample size was calculated using ARTMENU in STATA release 10.0 based on the following:

- Patients will be recruited over 3 years and followed up for a further 10 years

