- Exponential time to conversion with a constant event rate of at least 1% per year without treatment
- Conversion hazard ratio (drug response) of control to treatment is 1.5 (1 year conversion rate 1% no or standard treatment vs 0.66% in the treated patients)
- Power = 80% (2-sided test at 5% level of significance)
- No interaction between the effects of aspirin and PPI interventions
- A 10% loss to follow-up from Office of National Statistics flagging

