An economic analysis will be undertaken which compares the mean per patient cost of the alternative trial arms using resource use data collected in the trial and appropriate UK unit costs. Differential costs could then be related to conversion to BA. To increase the value to decision makers, the economic data collected in the trial could be synthesised with other evidence by relating long-term (lifetime) health service costs to long-term quality-adjusted life expectancy. The analysis would be based on a state transition model, which would characterise how patients progress from BM to dysplasia and to BA competing risk of death. The annual cost and health-related quality of life associated with each stage of the disease will be estimated using trial data collected and literature. In addition, some limited data collection in appropriate non-trial patients would be undertaken. Assessments will be completed at baseline and every two years at the time of endoscopy.

- To assess whether intervention with PPI and/or aspirin induces changes in the expression of molecular markers for BA. To assess the genomics of aspirin sensitivity (efficacy and side effects)

ANALYSIS: Based on analysis of the samples, this aim will be carried out after the end of the trial under a separate analysis plan.

- To assess how quality of life is affected by the different treatments.

It was not possible to collect quality of life across time and so this secondary cannot be completed.

AspECT

A phase III randomised study of Aspirin and Esomeprazole chemoprevention in Barrett's metaplasia

Funded by CR-UK, MRC, UHL and NCI

ISRCTN No.85156844

- We will also assess what the biological risk factors are for cardiac disease and aspirin resistance.

Cardiac disease will be ascertained from SAE. The risk factors to be tested are hypercholesterol, family history of cardiac disease, patient history of cardiac disease, hypertension, diabetes or smoking. A logistic model predicting cardiac disease using these factors will be built. To consider aspirin resistance, a logistic model predicting cardiac disease in those taking aspirin will be built and described.

These 2 models will be repeated for the data from the time of the new tumour questions using cancer instead of cardiac disease.

- To assess if gender is prognostic for conversion or survival

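### The primary comparisons are re-run in men and in women with no treatment-by-sex interaction test; if the planned effect is real and equal in both, one sex alone is significant more often than not.

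*SAP*

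**What the plan says.** SAP 8.5, the section on pre-specified subgroups, contains one item: the combined analysis "will be repeated on males only and on just the females". SAP section 7 is softer and says only that the whole analysis may be repeated by sex. The analysis to be repeated is that of SAP 8.2: Kaplan-Meier curves, a logrank table with p-values at the 0.05 level, AFT time ratios with 95% confidence intervals (the definitive result), and Cox models if proportional hazards hold. SAP 8.3 makes no multiplicity adjustment.

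Sex appears in two other places. SAP 8.6 adds it as a covariate in a sensitivity model. SAP 2.1 lists the secondary objective "To assess gender differences in outcomes", which SAP section 9 turns into "To assess if gender is prognostic for conversion or survival". That analysis uses a logrank test and AFT and Cox models for the effect of sex, then adds treatment to the models; no product term is mentioned.

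The one formal interaction test in the SAP is aspirin by PPI (8.6), where the SAP also acknowledges low power. Treatment by centre is examined informally in 8.7, with a warning that chance differences are to be expected. Treatment by sex has neither a test nor a warning.

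**The concern.** Two separate significance tests do not test whether two effects differ. With about four men to every woman, the male analysis has far more events. The two p-values can fall on opposite sides of 0.05 through sample size alone, and the plan gives no rule for reading such a result.

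At stake is a conclusion that aspirin or high-dose PPI works in one sex only, drawn from data that show no such thing. A male-only benefit would look plausible to many readers, because Protocol 1.5 cites a 3 to 1 male excess of oesophageal adenocarcinoma. The interaction term needs to be in the plan beforehand: under SAP section 10 anything not specified is exploratory, and a test added after the split p-values are known carries less weight.

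**Working it through.** **Inputs**
- Men 2012, women 501, total 2513 (Protocol section 2). Share of women: 501/2513 = 19.9%.
- "Power = 80% (2-sided test at 5% level of significance" and "Conversion hazard ratio (drug response) of control to treatment is 1.5" (SAP 2.5.3). The original calculation used 1.4 (SAP 2.5.2).
- "A total of 2224 patients (196 events) (approximately 556 in each intervention group" (SAP 2.5.3). Protocol 14.1 plans the final analysis to "be when there are at least 200 events and a median of at least 5 years follow up".
- Events by sex are in neither document. **Assumption:** proportional to patients, with a range of 10% to 25% in women.

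**1. Reproduce the plan's 196 events.** Freedman: (1.960 + 0.842)² × [(1.5 + 1)/(1.5 − 1)]² = 7.849 × 25 = 196.2. Schoenfeld: 4 × 7.849/(ln 1.5)² = 31.40/0.1644 = 191. The plan's figure is confirmed.

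**2. Split the events.** Men 196 × 2012/2513 = 156.9; women 196 × 501/2513 = 39.1.

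**3. Power within each sex.** With equal allocation, power ≈ Φ(ln HR × √d/2 − 1.960), plus a negligible opposite tail.
- HR 1.5, men: 0.4055 × √156.9/2 = 2.540, so Φ(0.580) = 71.9%.
- HR 1.5, women: 0.4055 × √39.1/2 = 1.267, so Φ(−0.693) plus the opposite tail = 24.5%.
- HR 1.4: men 55.9%, women 18.3%.

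**4. Chance that exactly one sex reaches p<0.05.** The sexes are independent, so this is pM(1 − pW) + (1 − pM)pW.
- HR 1.5: 0.719 × 0.755 + 0.281 × 0.245 = 0.543 + 0.069 = 61.2%.
- HR 1.4: 0.559 × 0.817 + 0.441 × 0.183 = 0.456 + 0.081 = 53.7%.

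| True HR, same in both sexes (196 events) | Exactly one sex at p<0.05 |
|---|---|
| 1.0 | 9.5% |
| 1.2 | 25.9% |
| 1.3 | 40.8% |
| 1.4 | 53.7% |
| 1.5 | 61.2% |
| 2.0 | 42.0% |

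The chance exceeds one half for a true HR between about 1.37 and 1.87.

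**5. Sensitivity at HR 1.5.**
- Women contribute 10% of events: power 76.8% and 14.6%, result 69.0%.
- Women contribute 25%: power 69.1% and 29.5%, result 57.8%.
- 200 events in total: 61.4%.
- Totals from 150 to 400 (an illustrative range): about 55% to 63%.

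**6. What the interaction test offers.** If the effect is identical, a two-sided 5% interaction test declares a difference 5% of the time, whatever the common HR. SE of the log ratio of hazard ratios = √(4/156.9 + 4/39.1) = √0.1278 = 0.36. For 80% power the ratio must be exp(2.802 × 0.358) = about 2.7.

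The events-based formula approximates the AFT analysis that the SAP calls definitive.

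**The case against.** The plan has a reason for looking at each sex. The trial first accrued only men, women were added for generalisability, and the sexes were minimised separately (SAP 2.4 and 2.6), so a male-only run recovers the population first targeted. Nothing in the SAP says that p-values will be compared between sexes. Time ratios with confidence intervals are the definitive output, and from two independent estimates a reader can work out their ratio. The interaction test could detect only a very large difference. All of this stands, but it does not remove the gap: p-values at 0.05 are also planned in each sex, with no guidance on how to read them.

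Three stronger readings are tempting, and the documents do not support them.
- A reader might infer that a split result is likely whatever the true effect. The table shows otherwise for null, small and large effects.
- A reader might infer that significance in men only is the usual outcome. At 196 events that pattern has a 54% chance at HR 1.5, but 46% at HR 1.4, and 49% at HR 1.5 if women contribute a quarter of events. A female estimate in the wrong direction is unlikely at HR 1.5, at about 10%.
- A reader might infer that the gender objective goes unanswered. It concerns outcomes; the SAP reads it as a prognostic question and specifies models for it.

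**Conclusion.** The gap is real. Separate-sex treatment comparisons with p-values are planned, and no treatment-by-sex interaction is specified in either document. If the planned effect is real and identical in both sexes, the chance that exactly one sex is significant is about 61% at HR 1.5 (58% to 69% for a female event share of 25% to 10%) and 54% at HR 1.4.

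These figures rest on the assumed event split and on taking an apparent difference to mean p<0.05 in one sex but not in the other. They apply to each comparison with about 196 events. Patients randomised to PPI dose only are left out of the aspirin comparison (SAP 2.2 and section 7), so its male and female groups are smaller than 2012 and 501 by a number the documents do not give. The pooled primary analysis is not affected; the weakness lies in how the sex-specific results may be interpreted.

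**What to change.** In SAP 8.5:
- Add a treatment-by-sex product term to the AFT model for each co-primary, and to the Cox model if proportional hazards hold.
- Report the ratio of time ratios, women to men, with its 95% confidence interval, and base any claim of a sex difference in treatment effect on that.
- Show the estimates in men and in women with confidence intervals, as description and without separate significance claims.
- State that the interaction test has low power (SE about 0.36 on the log hazard-ratio scale at 196 events), so a non-significant result does not show that the effects are equal.
- Bring the wording of section 7 into line with 8.5 on whether the separate-sex analyses will or may be done.

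The cost is a few lines of SAP text and one extra term in models already planned. No new data are needed.

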8.6 Sensitivity analysis

As specified in section 7 using PP sample and variables as randomised.

A Kaplan-Meier plot will be drawn with a line for each of the four treatment groups to look for a visual sign of interaction between the treatments. An interaction term will also be added to AFT and COX models containing both of the treatment main effect to test for significance (although this will have low power). If statistically significant interaction is found, the results will also be presented for aspirin within each PPI treatment group and for PPI within each aspirin group.

The estimate of the treatment effect in AFT and Cox models will be adjusted for presence of helicobacter.

AFT and Cox models will be adjusted for gender as well as the minimisation variables.

AFT and Cox models will be adjusted for NSAID and for Cox Inhibitor use. Use will be defined as more than 1 month continuously and as more than 6 months continuously.

AFT and Cox models with stratifying variables will be redone using actual Barrett's length at baseline.

The primary analysis will be repeated using all oesophageal cancers instead of just adenocarcinoma of the oesophagus.

The primary analysis will be repeated censoring follow-up when patients start taking NSAID.

The primary analysis for PPI will be repeated censoring patients when they start taking another medicine for Barrett's (data in EOT form reasons for withdrawal 'other' and in Follow Up form in 'treatments for Barrett's other than esomeprazole').

8.7 Treatment by Centre Interaction

Consistency of effect will be assessed across the centres by informal examination of the within centre effects. There will be limited capacity to investigate these formally and it is noted that such centre effects are expected by chance.

8.8 Supporting information

The withdrawal rates from aspirin and PPI will be described as well as the dose of drug taken at time points throughout the trial.

9. Analysis to address secondary aims

There are many secondary aims so these will be described under each aim

- To assess whether intervention with aspirin results in decreased high-grade dysplasia, in decreased all cause mortality, in decreased adenocarcinoma oesophageal cancer incidence, and in decreased cause-specific mortality when each is considered separately

ANALYSIS: As for primary using the AFT model. As for primary using COX model for all cause mortality. For the COX model for high grade dysplasia, adenocarcinoma oesophageal cancer incidence and cause-specific mortality a competing risks approach will be used since there are expected to be many competing deaths for these endpoints.

For oesophageal cancer, as a sensitivity, the analysis will be rerun including all oesophageal cancers rather than just adenocarcinomas.

- To assess whether intervention with high dose PPI results in decreased high-grade dysplasia, in decreased all cause mortality, in decreased oesophageal cancer incidence and in decreased cause-specific mortality when each is considered separately

ANALYSIS: As for primary using the AFT model. As for primary using COX model for all cause mortality. For the COX model for high grade dysplasia,

AspECT

A phase III randomised study of Aspirin and Esomeprazole chemoprevention in Barrett's metaplasia

Funded by CR-UK, MRC, UHL and NCI

ISRCTN No.85156844

adenocarcinoma oesophageal cancer incidence and cause-specific mortality a competing risks approach will be used since there are expected to be many competing deaths for these endpoints.

For oesophageal cancer, as a sensitivity, the analysis will be rerun including all oesophageal cancers rather than just adenocarcinomas.

- Are there clinical and molecular risk factors than can be identified in BM for the development of BA?

ANALYSIS: Variables to be specified at the end of the trial. These variables of interest will be added to the accelerated failure time model with the event oesophageal adenocarcinoma and those found to be significant will be reported. The variables will also be considered in the competing risk COX approach.;

- What is the cost effectiveness of aspirin and/or PPI treatment in the prevention of BA?

The analysis will not be undertaken by CSM; to be analysed by [name]. Information from protocol:

An economic analysis will be undertaken which compares the mean per patient cost of the alternative trial arms using resource use data collected in the trial and appropriate UK unit costs. Differential costs could then be related to conversion to BA. To increase the value to decision makers, the economic data collected in the trial could be synthesised with other evidence by relating long-term (lifetime) health service costs to long-term quality-adjusted life expectancy. The analysis would be based on a state transition model, which would characterise how patients progress from BM to dysplasia and to BA competing risk of death. The annual cost and health-related quality of life associated with each stage of the disease will be estimated using trial data collected and literature. In addition, some limited data collection in appropriate non-trial patients would be undertaken. Assessments will be completed at baseline and every two years at the time of endoscopy.

- To assess whether intervention with PPI and/or aspirin induces changes in the expression of molecular markers for BA. To assess the genomics of aspirin sensitivity (efficacy and side effects)

ANALYSIS: Based on analysis of the samples, this aim will be carried out after the end of the trial under a separate analysis plan.

- To assess how quality of life is affected by the different treatments.

It was not possible to collect quality of life across time and so this secondary cannot be completed.

AspECT

A phase III randomised study of Aspirin and Esomeprazole chemoprevention in Barrett's metaplasia

Funded by CR-UK, MRC, UHL and NCI

ISRCTN No.85156844

- We will also assess what the biological risk factors are for cardiac disease and aspirin resistance.

Cardiac disease will be ascertained from SAE. The risk factors to be tested are hypercholesterol, family history of cardiac disease, patient history of cardiac disease, hypertension, diabetes or smoking. A logistic model predicting cardiac disease using these factors will be built. To consider aspirin resistance, a logistic model predicting cardiac disease in those taking aspirin will be built and described.

These 2 models will be repeated for the data from the time of the new tumour questions using cancer instead of cardiac disease.

- To assess if gender is prognostic for conversion or survival

ANALYSIS: Using the survival time calculated for the primary objective, a logrank test to assess the effect of gender with both males and females in the sample will be reported in a table as for the primary objective. Create an AFT model looking at the gender effect adjusting for age, length of Barrett's and presence of intestinal metaplasia so that there is a time ratio with 95% confidence interval for the gender effect. Repeat with a Cox model if assumptions valid. Redo both of these models with treatment also included.

Exploratory aim

To assess aspirin's role on the development of colorectal adenomas and cancer

Use as outcome the time to colorectal cancer or colorectal adenoma. Using a logrank test, consider if aspirin use is prognostic.

To collect and bank samples for use in future ethically approved studies

To be analysed under other protocols and analysis plans.

And the exploratory uses of the data

- Describe Barrett's length over repeat biopsies and investigate a change in length from baseline to 2 years between treatment groups.

ANALYSIS: For all patients, assess if Barrett's metaplasia length shows a trend with time using repeated measures anova.

Using the baseline and 2 year length, compare the Barrett's length difference between treatment groups using paired ttest.

- Can intervention with aspirin result in a lower stage of adenocarcinoma ?
Can intervention with PPI result in a lower stage of adenocarcinoma ?

ANALYSIS: Chi square trend test on the following tables

AspECT

A phase III randomised study of Aspirin and Esomeprazole chemoprevention in Barrett's metaplasia

Funded by CR-UK, MRC, UHL and NCI

ISRCTN No.85156844

	No aspirin	Aspirin
None		
Stage I		
Stage II		
Stage III		
Stage IV		

	Low PPI	High PPI
None		
Stage I		
Stage II		
Stage III		
Stage IV		

Note: this ignores the different follow-up times

- Does adjustment for oesophagectomy, ablation therapy, endoscopic mucosal resection change the treatment effect ?

ANALYSIS: Within the multivariate AFT and COX models, add time dependent variables for the above and note the new treatment effect.

- Is the event rate different for those previous users of aspirin who were not randomised to it compared to previous users who continued with aspirin as their randomised treatment?

ANALYSIS: Kaplan-Meier curve and Logrank of the previous users of aspirin who were not randomised to it versus those randomised to aspirin.

- Investigation of the hypothesis that aspirin will have a chemopreventive effect on all epithelial cancers using the same mechanism it does to reduce oesophageal cancer, however, high dose PPI therapy may arguably increase colon cancer incidence as gastrin levels increase and this hormone is a known stimulant for colon cancer

ANALYSIS: Define outcome as time to epithelial cancer (oesophageal, colorectal, other gi or skin). For those randomised to aspirin and low PPI or to no aspirin and low PPI, use an AFT model with stratification variables to assess if aspirin is predicting outcome.

Where possible, all these analyses will use the ITT sample.

